17.2.2.2 Urine for *Legionella pneumophila* and *Streptococcus pneumoniae* Antigen Screening

At the Screening visit, urine will be collected to test for the presence of *Legionella pneumophila* and *Streptococcus pneumoniae* antigens. Testing will be performed at the local laboratory using kits supplied by the sponsor and the results will be recorded on the eCRF.

17.2.2.3 Serology for *Legionella pneumophila*, *Mycoplasma pneumoniae* and *Chlamydophila pneumoniae* Titers

At the Screening visit, and at the PTE visit, blood samples will be collected to conduct serology for *Legionella pneumophila*, *Mycoplasma pneumoniae* and *Chlamydophila pneumoniae* by the Central Laboratory.

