17.2.3.3 Clinical Evaluation of the Infection Under Study at PTE

The PTE assessment is to be performed 5 to 10 days after the subject's last day of therapy. The investigator will determine whether or not the subject meets the criteria of 1 of the following clinical outcomes:

Clinical Success: survival after completion of a test article regimen without receiving any systemic antibacterial therapy other than test article, resolution of signs and symptoms of the infection present at Screening with no new symptoms or complications attributable to CABP and no need for further antibacterial therapy.

Clinical Failure: the subject requires alternative antibacterial treatment for CABP prior to PTE related to either (a) progression or development of new symptoms of CABP or (b) development of infectious complications of CABP (eg, empyema, lung abscess).

- The subject is receiving antibiotics that may be effective for the infection under study for a different infection from the 1 under study.
- Death prior to PTE.

Indeterminate: the clinical response to test article could not be adequately inferred due to:

- Subjects were not seen for PTE evaluation because they withdrew consent, were lost to follow-up, other (specify).
- Other specified reason.

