22.1 Analysis Populations

A number of subject populations have been defined for the various analyses of efficacy and safety, as follows:

- The ITT population will consist of all randomized subjects.
- The microbiological intent-to-treat (microITT) population will consist of subjects in the ITT population who have at least 1 causative pathogen identified at Screening from culture of a respiratory specimen (eg, respiratory fluid obtained by bronchoalveolar lavage or bronchoscopy; pleural fluid obtained by thoracentesis; or expectorated or induced sputum meeting adequacy criteria), culture of blood, or from a culture-independent method (eg, positive urinary antigen test for *Streptococcus pneumoniae* or *Legionella pneumophila*, or positive serology for *Legionella pneumophila*, *Mycoplasma pneumoniae* or *Chlamydophila pneumoniae*).
- The CE population will consist of all ITT subjects who received test article, have a qualifying CABP, an assessment of outcome, and meet all other evaluability criteria detailed in the SAP.
- The microbiologically evaluable (ME) population will include subjects in the CE population who have at least 1 causative pathogen at Screening.
- The Safety population will consist of all randomized subjects who receive test article.

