5 STUDY DESIGN CONSIDERATIONS

5.1 Study Design

This is a randomized (1:1), double-blind, active comparator-controlled, Phase 3 study comparing 7 to 14 days of treatment with either omadacycline or moxifloxacin for the treatment of adults with CABP. The number of subjects in Pneumonia Outcomes Research Team (PORT) Risk Class II will be limited to no more than 15% of randomized subjects. Subject randomization will be stratified across treatment groups by PORT Risk Class (II and III/IV), receipt of an allowed antibacterial therapy in the 72 hours prior to study treatment (yes and no) and geographic region (Western Europe/North America, Eastern Europe, and Rest of World). All subjects are expected to present with CABP severe enough to require a minimum of at least 3 days of intravenous (iv) treatment. After a minimum of 3 days of iv treatment, the investigator can switch the subject to oral (po) treatment if the subject is considered clinically stable and meets the criteria for transition to a po regimen.

Screening assessments will be performed within 24 hours before the first infusion of test article. The day of the first infusion of test article is defined as Day 1 and the day prior is Day-1; there is no Day 0. The study will have the following protocol-defined evaluations:

- Visits will be conducted daily on Days 1 through 7. The Day 6 visit is optional for subjects that have been switched to po test article and have been discharged from a hospital setting. A Day 10 visit should be conducted for subjects with treatment extending beyond 9 days, unless this visit coincides with the End of Treatment (EOT) Visit.
- EOT Visit: to be performed on the calendar day of, or within 2 days following the last dose of any test article. If a subject withdraws prematurely or terminates participation in the study before completion, the EOT Visit should be conducted.
- PTE Visit: to be performed 5 to 10 days after the subject's last day of study therapy
- Final Follow-up assessment: Study Day 30-37 (after start of first infusion of test article)

A detailed Schedule of Study Procedures is provided in [Appendix 1](#).

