Clinical Failure: the subject requires alternative antibacterial treatment for CABP prior to PTE related to either (a) progression or development of new symptoms of CABP or (b) development of infectious complications of CABP (eg, empyema, lung abscess). Other reasons for clinical failure are:

- The subject is receiving antibiotics that may be effective for the infection under study for a different infection from the one under study.
- Death prior to PTE.

Indeterminate: the clinical response to test article could not be adequately inferred due to:

- Subjects were not seen for PTE evaluation because they withdrew consent, were lost to follow-up, other (specify).
- Other specified reason.

Overall Clinical Response at PTE (based on the investigator's assessment) is determined as follows from the investigator's assessments at the EOT and PTE Visits:

Table 3. Investigator's Assessment of Clinical Response

EOT Visit	PTE Visit	Overall Assessment of Clinical Response at PTE Visit
Success	Success	Success
Success	Failure	Failure
Success	Indeterminate	Indeterminate
Failure	Success	Failure
Failure	Failure	Failure
Failure	Indeterminate	Failure
Indeterminate	Success	Indeterminate
Indeterminate	Failure	Failure
Indeterminate	Indeterminate	Indeterminate

Abbreviations: EOT = end of treatment; PTE = post-therapy evaluation.

For the ITT population, the proportion of ITT subjects with a Clinical Success is defined using the following formula (where the denominator adds to the total number of subjects in the ITT population):

Number of subjects with Clinical Success

(Number of subjects with Clinical Success + Number of subjects with a Clinical Failure + Number of subjects with an Indeterminate response)

By definition, subjects in the CE-EOT and CE-PTE populations cannot have an Indeterminate response. Thus, for the CE-EOT and CE-PTE populations, the proportion of subjects with a Clinical Success is defined using the following formula:

Number of subjects with Clinical Success

(Number of subjects with Clinical Success + Number of subjects with a Clinical Failure)

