In general, baseline is defined as the 24-hour period prior to the administration of the first dose of test article. However, if the subject is unable to produce a sputum sample at baseline or the sputum sample is not adequate based on the Gram stain criteria, a specimen obtained within 24 hours after the first dose of test article may be considered a baseline sample. If the sputum sample collected in the 24-hour period prior to the administration of the first dose of test article is not adequate based on the Gram stain criteria and the sputum sample obtained within 24 hours after the first dose of test article is not adequate based on the Gram stain criteria, only the sputum sample collected in the 24-hour period prior to administration of the first dose of test article will be considered baseline. UAT samples up through 24 hours after the first dose of test article may be considered the baseline sample, if a previous sample was

not taken or was found to be negative. Blood samples up through 24 hours after the first dose of test article may be considered the baseline sample, if a previous sample was not taken or was found not to have a pathogen.

The following isolates will always be considered a pathogen:

Streptococcus pneumoniae

- Positive BAL, bronchoscopy, pleural fluid, or blood culture; or
- Positive sputum culture in the presence of an adequate Gram stain defined as having > 25 polymorphonuclear neutrophils (PMNs)/Low Power Field (LPF) and < 10 Squamous Epithelial Cells (SECs)/LPF; or
- Positive urinary antigen test

Haemophilus influenzae

- Positive BAL, bronchoscopy, pleural fluid, or blood culture; or
- Positive sputum culture in the presence of an adequate Gram stain (> 25 PMNs/LPF and < 10 SECs/LPF)

Staphylococcus aureus

- Positive BAL, bronchoscopy, pleural fluid, or blood culture
- Positive sputum culture in the presence of an adequate Gram stain (> 25 PMNs/LPF and < 10 SECs/LPF)

Moraxella catarrhalis

- Positive BAL, bronchoscopy, pleural fluid, or blood culture; or
- Positive sputum culture in the presence of an adequate Gram stain (>25 PMNs/LPF and < 10 SECs/LPF)

Legionella pneumophila

- Positive BAL, bronchoscopy, pleural fluid, or blood culture; or
- Positive sputum culture, regardless of Gram stain findings; or
- Positive acute (baseline) or positive convalescent (PTE) IgM (Euroimmun IgM ELISA OD ratio of ≥ 1.1)

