- Negative acute (baseline) and positive or indeterminate convalescent (PTE) IgG (Euroimmun IgG ELISA OD ratio of ≥ 1.1)
- A positive urine antigen test

Mycoplasma pneumoniae

- Positive acute (Baseline) or positive convalescent (PTE) IgM (Euroimmun IgM ELISA OD ratio of ≥ 1.1)
- Negative acute (Baseline) and positive or indeterminate convalescent (PTE) IgG (Euroimmun IgG ELISA OD ratio of ≥ 1.1)

Chlamydophila pneumoniae

- Positive acute (Baseline) or positive convalescent (PTE) IgM (SeroCP™ IgM cut-off index of > 1.5)
- Negative acute (Baseline) and positive or indeterminate convalescent (PTE) IgG (SeroCP™ IgG cut-off index of > 1.1)

The following isolates are considered as contaminants from respiratory specimens rather than pathogens of CABP: fungi, *Enterococcus* spp., viridans streptococci, coagulase-negative staphylococci, *Micrococcus* spp., *Neisseria* spp. other than *N. meningitidis*, *Corynebacterium* spp. and other coryneforms, *Lactobacillus* spp., *Vibrio* spp., *Capnocytophaga* spp., *Cardiobacterium* spp., *Flavobacterium* spp.

Other isolates identified from culture of blood and respiratory specimens will be reviewed in a blinded manner by the Sponsor on a case-by-case basis for determination of whether the organism is a pathogen for CABP.

An expanded microITT population will also be analyzed. The expanded microITT population will be defined using the same criteria as for the microITT population except an adequate Gram stain will be defined as > 10 PMNs/LPF and < 10 SECs/LPF for determination of whether an isolate from a sputum culture is a pathogen or not.

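### microITT admits atypical-pathogen cases on serology drawn at PTE, so PTE results in convalescent-only cases omit the non-successes who never reached that visit

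*Combined protocol and SAP*

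**What the plan says.** Protocol v2.0 Section 22.1 defines microITT as "subjects in the ITT population who have at least 1 causative pathogen identified at Screening" and lists positive serology among the qualifying methods. The opening paragraph of SAP 6.1.3 likewise requires the pathogen to be found at baseline. Baseline there is the 24 hours before the first dose, with a 24-hour extension after it for certain sputum, urinary antigen and blood samples.

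The organism-by-organism list in SAP 6.1.3 goes further for the three atypical pathogens. A "Positive acute (baseline) or positive convalescent (PTE) IgM" is enough, and so is "Negative acute (baseline) and positive or indeterminate convalescent (PTE) IgG". The same two routes apply to Mycoplasma and Chlamydophila, with different assay cut-offs for Chlamydophila.

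Protocol Section 17.2.2.3 fixes the two sampling times: "At the Screening visit, and at the PTE visit, blood samples will be collected to conduct serology". SAP 5.1 places PTE relative to the end of treatment: it is "to be performed 5 to 10 days after the subject's last day of study therapy".

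On outcome, SAP 5.2.2.1 lists "Death prior to PTE" as Clinical Failure and classes a subject not seen at PTE as Indeterminate. SAP 8.3 keeps Indeterminates in the microITT denominator, where they count as failures.

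**The concern.** Membership of an ITT-type population should not depend on what happens after randomisation. Here one entry route needs a blood sample from a visit that also determines the outcome. For a case identified only by convalescent serology, the deaths before PTE and missed visits that SAP 8.3 means to count against the treatment never reach the denominator.

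Several results inherit this:

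- **PTE response** in microITT, overall and by pathogen (SAP 10.3, 10.4 and Appendix 2). Response by causative pathogen is a stated secondary objective.
- **Microbiological response.** SAP 5.2.2.2 allows a pathogen identified only by serology no more than a presumed or indeterminate response, so its result simply follows the clinical one.
- **ME-PTE.** SAP 6.1.4.5 deliberately keeps EOT failures, and deaths between EOT and PTE, in CE-PTE without an in-window PTE visit. ME-PTE also requires microITT membership (SAP 6.1.5), so those failures drop out again when only convalescent serology could have identified the pathogen.

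Nothing elsewhere offsets this. SAP 8.3 has no rule for an absent convalescent sample. The expanded microITT changes only the Gram-stain threshold, and no analysis restricted to baseline evidence is planned.

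**Working it through.** **The plan's own figure.** SAP Table 1 expects 27% of 750 subjects in microITT: 0.27 × 750 = 202.5, stated as 202. With 101 per arm, 80% success in both arms, a 15% margin and one-sided alpha 0.025 (stated for the ITT column, assumed here for microITT), the Farrington-Manning method gives 74.9% power against the stated 74%. The figure reproduces.

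**Are all the excluded subjects non-successes at PTE?** SAP Table 3 has three rows with an Indeterminate PTE. Paired with EOT Success, Failure and Indeterminate, they give Indeterminate, Failure and Indeterminate. None gives Success, and death before PTE is Failure. So a subject without a PTE visit is never a PTE success. A subject who attends but has no blood drawn could be one, so m below counts only cases with no PTE visit.

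**PTE response in the convalescent-only subset.** Let p be the success rate among all cases that paired serology would identify, and m the fraction with no PTE visit. All successes are retained and a fraction m of the denominator is lost, so the observed rate is p/(1 − m). I take p = 0.79, the plan's PTE rate for ITT (the plan gives none for microITT). The documents give no value for m.

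- m = 5%: 0.79/0.95 = 83.2%
- m = 8%: 0.79/0.92 = 85.9%
- m = 10%: 0.79/0.90 = 87.8%

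That is 4 to 9 points too high.

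**PTE response in microITT overall.** Let s be the share of the 202 who qualify only by convalescent serology, also an assumption. The observed overall rate is (1 − s) × 0.79 + s × 0.79/(1 − m), and the non-successes removed number 202 × s × m/(1 − m).

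| s | m = 5% | m = 8% | m = 10% |
|---|---|---|---|
| 10% | 79.4% (1.1 removed) | 79.7% (1.8) | 79.9% (2.2) |
| 30% | 80.2% (3.2) | 81.1% (5.3) | 81.6% (6.7) |
| 40% | 80.7% (4.3) | 81.7% (7.0) | 82.5% (9.0) |

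**Early Clinical Response.** This is fixed at 72 to 120 hours, so some subjects lost later were early successes. With q the early success rate among those lost, the observed rate is (0.79 − m × q)/(1 − m). At m = 10%:

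- q = 0.5: 0.74/0.90 = 82.2%, or 3.2 points high
- q = 0.79: no bias
- q = 0.9: 0.70/0.90 = 77.8%, or 1.2 points low

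**Between-arm difference at PTE, within the subset.** Suppose m is 10% on omadacycline and 5% on moxifloxacin, and the extra losses are the only true difference (75% against 80%). The observed rates are 0.75/0.90 = 83.3% and 0.80/0.95 = 84.2%, so a true −5.0 points appears as −0.9. If the true rates are both 80% with the same m values, the observed difference is 0.80/0.90 − 0.80/0.95 = +4.7 points. With equal rates and equal m there is no bias in the difference.

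**The case against.** Paired serology is scheduled in the protocol, and the PTE blood sample is given no other use there. SAP 5.2.2.2 also speaks of acute and convalescent serology together. Identification at Screening can fairly be read as infection present at Screening and confirmed later. This stands: a reader might infer that the SAP departs from the protocol without declaring it in SAP Section 7, but the documents do not establish that. They show loose wording.

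Much of the loss is already visible. SAP 9.1 tabulates missed PTE visits with reasons, and exclusions from each population, by arm. SAP 9.2.1 lists serology findings, and all-cause mortality is analysed in full ITT. This also stands, but those displays count absences. They do not show what the pathogen results look like without the convalescent route.

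A reader might infer that failures in general are shut out. They are not. Discontinued subjects should attend PTE if possible (protocol Section 26), and a failure who attends can qualify. Cases with culture, urinary antigen or acute IgM evidence are untouched.

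A reader might also infer that early stoppers have too little time to seroconvert. PTE does fall (last dose day − 1) + 5 to 10 days after Day 1: 7 to 12 days after a Day 3 stop, against 18 to 23 days after a 14-day course. The documents say nothing about antibody timing, so no size can be attached to this.

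**Conclusion.** The concern holds for PTE clinical response, the presumed microbiological response that follows it, and by-pathogen PTE results, in cases identified only by convalescent serology. The direction is upward. The size, about 83% to 88% in that subset and about 80% to 82% in microITT overall for a true 79%, rests on two assumed inputs: m of 5% to 10% and s of 30%. Over s from 10% to 40% the overall figure runs from 79.4% to 82.5%.

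Two stronger readings are not supported. One is that Early Clinical Response is inflated by the same 4 to 9 points. That calculation needs every lost subject to be a non-success, which is true only at PTE. For the early endpoint the effect is probably smaller, and even its sign depends on who is lost. The other is that the treatment comparison is compromised. Bias in the difference under equal true rates needs loss to PTE to differ between arms, and the documents give no reason to expect that in a double-blind trial.

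The primary ITT analysis is unaffected, and the SAP specifies no non-inferiority conclusion in microITT. This is a cheap improvement to the results that serve a stated secondary objective.

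**What to change.** Keep the paired-serology definition of microITT and leave the expanded microITT as it is. Moving convalescent-only cases into the expanded set would mix two changes in one population, and Appendix 2 plans no overall PTE response or microbiological response there.

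- In SAP 10.3, 10.4 and Appendix 2, add a sensitivity analysis that repeats the microITT Early Clinical Response, PTE response and by-pathogen tables in subjects with baseline evidence only: culture, urinary antigen or acute IgM.
- In the by-pathogen tables, show convalescent-only atypical cases on separate rows, labelled as conditional on a PTE sample.
- Report the number of missing convalescent samples by arm.
- In SAP 6.1.3, state that identification at baseline includes identification by PTE serology.

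The cost is some SAP wording and a few more tables; no new samples are needed. The baseline-evidence set will contain fewer atypical cases, so its by-pathogen estimates will be less precise.

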6.1.3 Microbiological Intent-to-Treat (microITT) Population

The microITT population will consist of all subjects in the ITT population who have at least one causative bacterial pathogen identified from a culture of a respiratory specimen (eg, respiratory fluid obtained by bronchoalveolar lavage [BAL] or bronchoscopy; pleural fluid obtained by thoracentesis; or expectorated or induced sputum meeting adequacy criteria as defined by the Gram stain results), culture of blood or from a culture-independent method (eg, positive urinary antigen test for *Streptococcus pneumoniae* or *Legionella pneumophila*, or positive serology for *Legionella pneumophila*, *Mycoplasma pneumoniae*, or *Chlamydophila pneumoniae*) at baseline.

Pathogen determination of typical bacteria is based on the genus and species identification from the central laboratory. If the local laboratory grows an acceptable pathogen but the central laboratory is not able to grow the isolate, if isolates are lost during transportation or storage, or there are major discrepancies between the local and central laboratory in the identification of species, the central laboratory or other Sponsor designee will request that the local laboratory resend the isolate. If the central laboratory cannot determine the genus and species of the isolate for any reason, the local laboratory determination of genus and species will be used for pathogen identification. The central laboratory identification of genus and species is used for analysis unless no central determination exists in which case the local laboratory determination is used.

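### SAP 6.1.3 lets an indeterminate convalescent IgG establish an atypical pathogen, against its own positive-serology route and, for Legionella and Mycoplasma, against its printed cut-off

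*Combined protocol and SAP*

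**What the plan says.** The opening of SAP 6.1.3 defines microITT by at least one causative bacterial pathogen. Among the culture-independent routes it names "or positive serology for *Legionella pneumophila*, *Mycoplasma pneumoniae*, or *Chlamydophila pneumoniae*) at baseline". Protocol 22.1 uses the same phrase, "or positive serology for", for the same three organisms and does not mention indeterminate results.

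The organism rules follow later in SAP 6.1.3 under the line "The following isolates will always be considered a pathogen". For all three atypical organisms the IgG bullet accepts a negative acute sample followed by a "positive or indeterminate convalescent (PTE) IgG". For Legionella the IgG rule is "Negative acute (baseline) and positive or indeterminate convalescent (PTE) IgG (Euroimmun IgG ELISA OD ratio of ≥ 1.1"). Mycoplasma has the same rule and the same cut-off. For Chlamydophila it is "Negative acute (Baseline) and positive or indeterminate convalescent (PTE) IgG (SeroCP™ IgG cut-off index of > 1.1"). The Legionella IgM rule, which Mycoplasma shares, accepts positive results only: "Positive acute (baseline) or positive convalescent (PTE) IgM (Euroimmun IgM ELISA OD ratio of ≥ 1.1").

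SAP section 7, which lists changes from the protocol, names only the addition of the expanded microITT population.

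**The concern.** A population rule has to yield one set of subjects. This one conflicts with the definition it is meant to carry out and, for two organisms, with the number printed in the same line. No negative, indeterminate or positive band is given for IgG, so two programmers could follow the text in good faith and build different microITT sets.

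The rule feeds microITT and expanded microITT directly, and ME through SAP 6.1.5. Clinical response by causative pathogen is a secondary objective (SAP 4.2). Under SAP 5.2.2.2 an atypical pathogen found only by serology can have only a presumed or indeterminate microbiologic response, so no later culture can correct a doubtful entry, and a clinical success becomes a presumed eradication. Subjects admitted without a real atypical infection would blur the atypical rows. If their response does not differ by arm, they would also pull the arms together.

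**Working it through.** **Step 1. The rules side by side (SAP 6.1.3).**

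| Organism | IgM result accepted | IgM cut-off | Convalescent IgG accepted (acute negative) | IgG cut-off |
|---|---|---|---|---|
| Legionella | positive | ≥ 1.1 | positive or indeterminate | ≥ 1.1 |
| Mycoplasma | positive | ≥ 1.1 | positive or indeterminate | ≥ 1.1 |
| Chlamydophila | positive | > 1.5 | positive or indeterminate | > 1.1 |

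**Step 2. Three ways to read an IgG bullet.** Take a subject with a negative acute IgG, an indeterminate convalescent IgG and no other route into microITT.

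- *The words govern and 1.1 is the positive threshold.* A result below 1.1 reported as indeterminate qualifies. This conflicts with both the printed number and the positive-serology route.
- *The number governs and 1.1 is the positive threshold.* The subject does not qualify, and the indeterminate option does nothing.
- *1.1 is the floor for indeterminate or better.* Words and number agree, but the threshold for a positive IgG is then unprinted and the conflict with positive serology remains. For Legionella and Mycoplasma the IgM bullets speak against this reading. For Chlamydophila it is open, because the IgM and IgG cut-offs differ.

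The conflict with positive serology therefore covers all three organisms. The conflict with the cut-off is shown for Legionella and Mycoplasma only.

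**Step 3. The plan's own microITT figures (SAP 5.1.1, Table 1).** Size: 750 × 0.27 = 202.5, stated as 202. Power: 101 per arm, 80% success in both arms, margin 15%. Table 1 gives no alpha for this column; one-sided 0.025 is assumed from the two-sided 95% CI in SAP 10.3. By Farrington and Manning, the constrained rates under the null are 0.706 and 0.856.

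- s0 = √[(0.706 × 0.294 + 0.856 × 0.144)/101] = 0.0572
- s1 = √[2 × 0.80 × 0.20/101] = 0.0563
- Power = Φ[(0.15 − 1.96 × 0.0572)/0.0563] = Φ(0.67) = 74.9%, against 74% stated.

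**Step 4. What misclassification would do, by assumption only.** Let f be the share of the 202 without a real atypical infection, and assume no difference between arms in those subjects. If the true difference among real cases were −15 points, the expected microITT difference is (1 − f) × (−15).

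| f (assumed) | Subjects of 202 | Expected difference | Chance that the 95% lower limit clears −15% |
|---|---|---|---|
| 0 | 0 | −15.0 | 2.5% |
| 5% | 10.1 | −14.25 | 3.3% |
| 10% | 20.2 | −13.5 | 4.3% |
| 20% | 40.4 | −12.0 | 7.1% |

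The table shows direction and rate of change. It does not estimate f, which the documents do not allow.

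**The case against.** The best defence is that positive serology appears only as an example of a culture-independent method, that Protocol 22 leaves the definition of populations to the SAP, and that the bullets simply give the example its working meaning. In part this stands: the sponsor may choose a wider rule. But an example of a positive result does not make an indeterminate one positive, and section 7 declares no widening.

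A second defence is that the printed number may govern, in which case no borderline subject enters. That is possible, and it is why the defect is a rule with two outcomes rather than proof that false cases get in.

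A reader might go further in three ways that the documents do not support.

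- *A count of false entries.* Assuming that 0.5 to 2% of paired sera drift per organism, with three organisms and 90% of 750 subjects paired, gives 675 × 3 × 0.005 = 10 to 675 × 3 × 0.02 = 41, or 5 to 20% of 202. Neither rate has a source in the documents. The sum also treats every drift as false and ignores subjects who drift on two organisms or already qualify by another route.
- *An inverted rule.* Negative to indeterminate qualifies by IgG, while indeterminate to positive does not. Requiring a negative acute sample is nevertheless a restriction, and a subject who starts indeterminate can still qualify by a positive IgM at either visit or, for Legionella, by culture or urine antigen.
- *A threat to the trial's conclusion.* The primary analysis is Early Clinical Response in ITT (SAP 10.1). SAP 10.3 gives microITT a confidence interval but no non-inferiority rule, so the last column of the Step 4 table describes a test that the plan does not call for.

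Some traceability exists: SAP 9.2.1 provides a listing by testing modality that includes serology. The blinded review in SAP 6.2 covers pathogen determination, but the inputs it names for isolates are Gram stain and species identification, and these organism rules are stated as automatic.

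**Conclusion.** The point holds as an internal contradiction in a population definition and should be corrected. The wording occurs three times, so it is unlikely to be a stray slip. Which subjects belong in microITT depends on whether words or number govern, and for Chlamydophila on what an index of 1.1 means for that assay.

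The reach is limited to microITT, expanded microITT, ME and the atypical by-pathogen results. Rows for typical bacteria and the primary ITT analysis do not change. The size cannot be derived, because the documents report neither indeterminate IgG frequencies nor assay specificity. The 5 to 20% shares in the working are assumptions, and they matter only if indeterminate results are in fact admitted.

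**What to change.** Before unblinding, delete the indeterminate option from the three IgG bullets in SAP 6.1.3, so that the rule is negative acute and positive convalescent IgG. Confirm that each printed cut-off is the assay's positive threshold. This matters most for SeroCP IgG > 1.1: if that value is the floor of an indeterminate range, deleting the words alone would relabel indeterminate results as positive.

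If the sponsor means to keep indeterminate results, print the indeterminate band for each assay, declare the widening in SAP section 7, and add a microITT and by-pathogen sensitivity analysis without subjects who qualify only on an indeterminate IgG.

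Do not widen the acute criterion to negative or indeterminate. No minimum rise is required, so that change would let in a new borderline group just crossing the cut-off.

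The cost is three bullets, an assay check and possibly a slightly smaller microITT. As an assumed range, with equal arms and the Step 3 inputs, removing 5%, 10% or 20% of the 202 would take power from 74.9% to 72.7%, 70.4% or 65.2%. With no non-inferiority rule for microITT in SAP 10.3, that loss is one of precision only.
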